**SECTION H - ALCOHOL AND DRUG USE**

**READ and HEARD:** Now we are going to ask you some general questions regarding alcohol and drug use. Some types of alcohol or drug use can be related to the risk of becoming infected with HIV or HBV. Once again, the following questions are intended to help us determine how to improve the safety of donated blood. We are asking you to respond as truthfully as you can. The answers are confidential. Your individual responses will not be known by SANBS. Your answers will be reported together with all other people who complete the questionnaire.

H1. How often do you drink beer, wine, liquor, or mixed drinks? (Choose one)

- |    |                             |                   |
|----|-----------------------------|-------------------|
| 0  | Never                       | Skip to H4 |
| 1  | 1-3 times per month or less |                   |
| 2  | 1-2 times per week          |                   |
| 3  | 3-6 times per week          |                   |
| 4  | Everyday                    |                   |
| 97 | Don't Know                  |                   |
| 98 | Refuse to Answer            |                   |

H2. On average how many drinks do you have each time you drink? (When answering, one drink is a glass of wine or a beer or a mixed drink.)

Number of drinks         

997 Don't Know

H3a. Have you ever used dagga, marijuana, or hashish? (Choose one)

- |    |                  |                    |
|----|------------------|--------------------|
| 0  | No               | Skip to H4a |
| 1  | Yes              |                    |
| 97 | Don't Know       |                    |
| 98 | Refuse to Answer |                    |

H3b. When was the first year you used dagga, marijuana or hashish?

— — — — YYYY

2097 Don't Know (Year)

2098 Refuse to Answer (Year)

***If H3b is less than B2 then READ and HEARD: "The year that you entered for first year of dagga, marijuana, or hashish drug use is smaller than the year you were born. Please correct the year of your first dagga, marijuana, or hashish drug use." (Returns to H3b)***

H3c. When was the last year you used dagga, marijuana or hashish?

— — — — YYYY

2097 Don't Know (Year)

2098 Refuse to Answer (Year)

***If H3c is less than H3b then READ and HEARD: "The year that you entered for last year of dagga, marijuana, or hashish drug use is smaller than the year of your first reported dagga, marijuana, or hashish drug use. Please correct the last year of your dagga, marijuana, or hashish drug use." (Returns to H3c)***

H4a. Have you ever used whoonga which is also known as nyaope? (Choose one)

0 No **Skip to H5a**

1 Yes

97 Don't Know

98 Refuse to Answer

H4b. When was the first year you used whoonga or nyaope?

— — — — YYYY

2097 Don't Know (Year)

2098 Refuse to Answer (Year)

**If H4b is less than B2 then READ and HEARD: "The year that you entered for first year of whoonga or nyaope drug use is smaller than the year you were born. Please correct the year of your first whoonga or nyaope drug use." (Returns to H4b)**

H4c. When was the last year you used whoonga or nyaope?

— — — —      YYYY

2097      Don't Know (Year)

2098      Refuse to Answer (Year)

**If H4c is less than H4b then READ and HEARD: "The year that you entered for last year whoonga or nyaope drug use is smaller than the year of your first reported whoonga or nyaope drug use. Please correct the last year of your whoonga or nyaope drug use." (Returns to H4c)**

H5a. Have you ever used any non-injected drugs (drugs that are smoked, snorted or taken orally), examples include tik, mandrax, "glue", cocaine (crack), methamphetamines (crystal), ecstasy ("E") and LSD? (Choose one)

0      No      **Skip to H7**

1      Yes

97      Don't Know

98      Refuse to Answer

H5b. When was the first year you used non-injected drugs?

— — — —      YYYY

2097      Don't Know (Year)

2098      Refuse to Answer (Year)

**If H5b is less than B2 then READ and HEARD: "The year that you entered for first year of non-injected drug use is smaller than the year you were born. Please correct the year of your first non-injected drug use." (Returns to H5b)**

H5c. When was the last year you used non-injected drugs?

— — — —      YYYY

2097      Don't Know (Year)

2098      Refuse to Answer (Year)

***If H5c is less than H5b then READ and HEARD: "The year that you entered for last year non-injected drug use is smaller than the year of your first reported non-injected drug use. Please correct the last year of your non-injected drug use." (Returns to H5c)***

H6. If you have smoked or snorted drugs, did you share pipes or straws with another person? (Choose one)

1      Always

2      Sometimes

3      Never

97      Don't Know

98      Refuse to Answer

H7a. Have you ever used injection drugs (examples include heroin, cocaine, and amphetamines)? (Choose one)

0      No

1      Yes

97      Don't Know

98      Refuse to Answer

H7b. When was the first year you used injected drugs?

- — — —      YYYY
- 2097      Don't Know (Year)
- 2098      Refuse to Answer (Year)

**If H7b is less than B2 then READ and HEARD: "The year that you entered for first year of injected drug use is smaller than the year you were born. Please correct the year of your first injected drug use." (Returns to H7b)**

H7c. When was the last year you used injected drugs?

- — — —      YYYY
- 2097      Don't Know (Year)
- 2098      Refuse to Answer (Year)

**If H7c is less than H7b then READ and HEARD: "The year that you entered for last year of injected drug use is smaller than the year of your first reported injected drug use. Please correct the last year of your injected drug use." (Returns to H7c)**

H8a. Have you ever injected yourself with any substances including vitamins, steroids, or hormones which were not prescribed by a doctor or nurse? (Choose one)

- 0      No                      **Skip to Section I**
- 1      Yes
- 97      Don't Know
- 98      Refuse to Answer

H8b. Have you ever shared needles or syringes with another person to inject yourself with any substance including drugs, vitamins, steroids or hormones which were not prescribed by a doctor? (Choose one)

0 No

1 Yes

97 Don't Know

98 Refuse to Answer

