**SECTION B - DEMOGRAPHIC DATA**

**APPEARS ON SCREEN and HEARD if ACASI: This study has been approved by Ethical Committees in South Africa and the USA. This study also has been approved by the Office of Management and Budget; OMB XXXX, OMB approval expires XX, XXXX, 201X.**

**APPEARS ON SCREEN and HEARD if ACASI: We are asking you to respond as truthfully as you can. Please keep in mind that the questions are part of a scientific study, and the researchers will make every effort to keep your responses confidential. However, there is a small chance that your responses may not be kept confidential, but your name is not collected on the questionnaire and your responses cannot be easily traced back to you. Please answer these questions to the best of your knowledge and as truthfully as you can. You may skip any questions that you are not comfortable answering.**

**In this section of the questionnaire the research assistant will show you how to use the computer to answer the interview questions. After completing this section, with help from the research assistant, you will be left to complete the interview in private. If you have any questions at any time or are unsure of what to do, please ask for help.**

B1. What is your gender? (Choose one)

- |    |                  |
|----|------------------|
| 1  | Male             |
| 2  | Female           |
| 3  | Transgender      |
| 97 | Don't Know       |
| 98 | Refuse to Answer |

B2. What is your birth year?

— — — —

- |      |                  |
|------|------------------|
| 9997 | Don't Know       |
| 9998 | Refuse to Answer |

B3. What is your birth month? (Choose one)

January

February

March

April

May

June

July

August

September

October

November

December

Don't Know

Refuse to Answer

B4. What is your birth day?

97 Don't Know

98 Refuse to Answer

B5a. What is your country of birth? (Choose one)

- 1 South Africa
- 2 Zimbabwe
- 3 Malawi
- 4 Mozambique
- 5 Swaziland
- 6 Botswana
- 7 Lesotho
- 8 Namibia
- 9 Nigeria
- 10 Other
- 97 Don't Know
- 98 Refuse to Answer

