**SECTION I - MEDICAL HISTORY**

**READ and HEARD:** *In the next set of questions we will ask about some medical treatments you may have had.*

I1. Have you ever had a blood transfusion? (Choose one)

- 0 No **Skip to I5**
- 1 Yes
- 97 Don't Know
- 98 Refuse to Answer

I2. How many transfusion episodes have you had?

— —

- 97 Don't Know
- 98 Refuse to Answer

I3. When was the first year you received a transfusion?

— — — —

- 9997 Don't Know
- 9998 Refuse to Answer

**If I3 is less than B2 then READ and HEARD:** *"The year that you entered for first year transfusion is smaller than the year you were born. Please correct the year of your first transfusion." (Returns to I3)*

14. When was the last year you received a transfusion?

— — — —

9997 Don't Know

9998 Refuse to Answer

***If 14 is less than 13 then READ and HEARD: "The year that you entered for last year of transfusion is smaller than the year of your first reported transfusion. Please correct the last year of your transfusion." (Returns to 14)***

15. Have you ever had minor or major surgery in a hospital, doctor's room, or dentist's office? (Choose one)

0 No ***Skip to 19***

1 Yes

97 Don't Know

98 Refuse to Answer

16. In the 6 months before your donation, have you had minor or major medical surgery in hospital? (Choose one)

0 No

1 Yes

97 Don't Know

98 Refuse to Answer

17. In the 6 months before your donation, have you had any surgical procedures in your doctor's room or office? (Choose one)

- 0 No
- 1 Yes
- 97 Don't Know
- 98 Refuse to Answer

18. In the 6 months before your donation, have you had any tooth extractions or another dental procedure at a dentist's office? (Choose one)

- 0 No
- 1 Yes
- 97 Don't Know
- 98 Refuse to Answer

19. Have you ever had an endoscopy (a medical test where a flexible tube is used to look inside of your throat and digestive system) or colonoscopy (a medical test where tube is used to look inside your colon/large intestine)? (Choose one)

- 0 No **Skip to I11**
- 1 Yes
- 97 Don't Know
- 98 Refuse to Answer

I10. In the 6 months before your donation, have you had an endoscopy or colonoscopy? (Choose one)

- 0 No
- 1 Yes
- 7 Don't Know
- 8 Refuse to Answer

I11. Have you ever been immunized / vaccinated against Hepatitis B?

- 0 No
- 1 Yes
- 97 Don't Know
- 98 Refuse to Answer

I11b. If yes, can you tell us your age when you were immunized/vaccinated against Hepatitis B?

\_\_\_\_\_ years old

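### The year checks in the risk questionnaire treat Don't Know and Refuse codes as real years, so a respondent who codes the first year of drug use or transfusion cannot record the last year

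*Protocol*

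**What the plan says.** In Protocol Appendix 7, Section H asks ever-users of dagga (H3), whoonga (H4), other non-injected drugs (H5) and injected drugs (H7) for the first and last year of use. The year items carry two non-answer codes, "2097 Don't Know (Year") and "2098 Refuse to Answer (Year"). Section I asks for the first and last year of transfusion (I3, I4), with 9997 and 9998 as the codes. The birth-year item in Section B, "B2. What is your birth year", also uses 9997 and 9998.

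Two kinds of check are printed:

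- First year against birth year: "If H3b is less than B2 then READ and HEARD", repeated for H4b, H5b and H7b, and for transfusion as "If I3 is less than B2 then READ and HEARD".
- Last year against first year: "If H3c is less than H3b then READ and HEARD", repeated for H4c and H5c, for injected drugs as "If H7c is less than H7b then READ and HEARD", and for I4 against I3.

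When a check fires, the respondent hears an error message and returns to the item just answered. For H3c the message is "Please correct the last year of your dagga, marijuana, or hashish drug use". No check sends the respondent back to the earlier item, and none mentions the codes.

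**The concern.** A less-than comparison between two years makes sense only if both are years. Here a missing-value code can stand on either side, and every code is numerically larger than any real year. A donor who does not recall when use began but knows when it ended gives an ordinary, informative answer. The printed rule calls that answer an error and rejects it.

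Section 4.4.1 says the questionnaire covers exposure ever and in the six months before the index donation. Section H has no six-month item on the donor's own drug use, and items I1 to I4 have none on transfusion. The last year is therefore the only recency information on these exposures, in a study of recently acquired infection. Section 4.9 itself warns that missing data are typically not missing completely at random; these rules would add missing values, and in one path would force a Don't Know to be recorded as a refusal.

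**Working it through.** The protocol gives no figure to reproduce, so the check is to run the printed rules as logic.

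Inputs, all from Appendix 7: codes 2097 (Don't Know) and 2098 (Refuse) in Section H; codes 9997 and 9998 for B2, I3 and I4. Rules: reject the first year if first < B2; reject the last year if last < first. Real years were taken as 1930 to 2017, an assumed range of 2017 − 1930 + 1 = 88 years. The result does not depend on the range, because every code exceeds every year in it.

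Section H (the same for H3, H4, H5 and H7):

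| Birth year | First | Last | Comparison | Result |
|---|---|---|---|---|
| 1985 | 2003 | 2014 | 2003 ≥ 1985; 2014 ≥ 2003 | passes |
| 1985 | 2097 | 2014 | 2014 < 2097 | last year rejected |
| 1985 | 2097 | 2097 | 2097 ≥ 2097 | passes |
| 1985 | 2098 | 2097 | 2097 < 2098 | Don't Know rejected |
| 1985 | 2098 | 2098 | 2098 ≥ 2098 | passes |
| 9998 | 2003 | – | 2003 < 9998 | first year rejected |
| 9998 | 2098 | – | 2098 < 9998 | Refuse rejected |

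Over all values:

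- First year 2097: 0 of 88 real last years pass; only 2097 and 2098 pass.
- First year 2098: 0 of 88 pass; only 2098 passes.
- Birth year 9997 or 9998: no real first year passes, and neither do 2097 and 2098. The check has no passing answer.

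Section I, where the codes match those of B2:

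- I3 = 9997: 0 of 88 real values of I4 pass; only 9997 and 9998 pass.
- I3 = 9998: only 9998 passes at I4.
- B2 = 9997: at I3 only 9997 and 9998 pass.
- B2 = 9998: at I3 only 9998 passes.
- So with a coded birth year there is a way through I3, but only by entering a code, which in turn bars every real year at I4.

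With a real birth year and a real first year the checks work as intended, and a coded last year is accepted.

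With each check run only when neither value is a code, every real last year is accepted after a coded first year, and every real first year after a coded birth year. A true error (first use 1980, birth 1985) is still caught.

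**The case against.** The strongest reply is that the appendix is not the program. Section 4.4.1 presents it as questionnaire content, the ACASI is still to be developed, and section 4.11 schedules development and pilot testing before enrollment. The text still has open drafting queries, for example at J14a and L5. The software might treat the codes as missing, and a repeating error message is something a pilot could well expose. This stands as a reason for a low grade. It does not remove the point: the appendix spells out the validation rules, and nothing in the protocol exempts the codes from them.

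The second reply concerns reach. Neither drug use nor transfusion is among the hypotheses in section 4 or the predictors named in section 4.9. Ever-use and ever-transfused are asked before the checks and are kept. A calendar year of last use maps only coarsely onto a six-month window. All of this stands.

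The third reply concerns birth year. B2 is answered with the research assistant at hand, and participants are already linked to their donor record. Withholding birth year is probably rare. This stands too.

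Stronger readings are tempting but not supported:

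- A reader might infer that a donor who withholds birth year cannot finish the interview, so that the rest of Section H and Sections I to L are lost. Respondents are told that they may skip questions and may call the assistant. The protocol does not say how a skipped item behaves in these checks, so the blockage is possible but not shown.
- A reader might extend the no-exit loop to transfusion. It does not arise there, because I3 shares its codes with B2.
- A reader might infer that everyone with imperfect recall is recorded as refusing. Don't Know after Don't Know passes; a forced Refuse arises only when an earlier item was itself refused. An approximate year entered in place of a code is unaffected.

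**Conclusion.** The point holds for the rules as printed, and it is minor. A respondent who codes the first year of drug use or transfusion cannot record a real last year. After a refused first year, even Don't Know is refused for the last year. A coded birth year leaves no passing answer at H3b, H4b, H5b or H7b, and at I3 leaves only a code.

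Among ever-users who code the first year, the loss of the last year is complete. As a share of all ever-users it equals the share who code the first year. The protocol gives no such rate: an assumed 10% would mean 10% lost for that substance and an assumed 30% would mean 30%, but neither figure has support in the document. Whether those respondents differ systematically from other users cannot be settled from it either.

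The conclusion assumes that the rules are programmed as written and the codes compared as numbers. The power calculations, the named hypotheses and the ever-use answers are not touched.

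**What to change.** Add one condition to each of the ten rules (H3b, H3c, H4b, H4c, H5b, H5c, H7b, H7c, I3, I4): compare the two years only when both are real years, that is, when neither is a Don't Know or Refuse code. For H3c the rule would read: if H3b and H3c are both real years and H3c is less than H3b, play the message and return to H3c.

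Test at least these (birth, first, last) combinations in the pilot: 1985, 2097, 2014 and 9998, 2003, 2014 should pass in Section H; 1985, 9997, 2014 should pass in Section I; birth 1985 with first year 1980 should still be rejected.

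The cost is a small edit to the specification before the ACASI is programmed and piloted. It adds no questions and no burden for participants. A last year rejected at interview cannot be recovered from these items afterwards.

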#### **4.1 Study Population**

We will conduct a case-control study of risk factors and molecular surveillance for incident HIV and HBV infections in blood donors in South Africa. Accrual, enrollment and follow-up is planned to occur during the period of 3 years (April 2014 – March 2017).

*Our Two Case Groups* will be: (1) 300 incident HIV infected SANBS blood donors, as established through either combined ID-NAT/serology (“NAT yield”) or LAg Avidity assay testing, and (2) 150 incident HBV infected SANBS blood donors, as established through combined ID-NAT/serology (“NAT yield”) and anti-HBc negative testing.

*Controls* will comprise a sample of up to 900 SANBS blood donors who are negative for all infectious markers for which SANBS currently tests and that (a) come from the same geographic areas as the cases (distributed across up to 5 of the 7 regional zones within SANBS) and will further be frequency matched for (b) population group (race), and (c) age. We will enroll three controls for each incident HIV case. These participants will serve as controls for HBV cases also.

*Prospective Cohort:* Approximately 50 persons with very recent HIV infection (NAT yield only) and up to 20 elite controllers identified during this study (mid-2014 – mid-2017) will also be eligible for enrollment in a six month prospective longitudinal study with samples collected for PBMC and other specimen preparations as soon possible after the index donation followed by additional specimen collection at 2, 3 and 6 months.

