The purpose of objective 1a is to identify the demographic and behavioural risk factors associated with incident HIV infection among blood donors in South Africa previously identified as “NAT-yield” and other recently acquired infection based on LAg Avidity testing as compared to controls. The outcome variable is whether or not a blood donor has HIV infection. That is, a binomial variable. The predictor variables believed to be associated with HIV in blood donors will include recent change in sexual partner, older male/younger female sexual partnership, a greater number of recent sexual partners, unprotected receptive anal intercourse, and lower socioeconomic status. Other possible predictor variables, e.g., behavioural variables, will be examined to understand their relationship to whether or not the blood donor has HIV infection. The association between the outcome variable and a predictor variable will be examined using categorical data analysis techniques. Bivariate analysis will be conducted using Chi-square tests. Analyses that include more than one predictor variable will be conducted using multiple logistic regression, which may include interaction terms. In addition, nonparametric modeling will be used when there are multiple predictor variables.

The purpose of objective 1b is to identify the demographic and behavioural risk factors associated with incident HBV infection among blood donors in South Africa previously identified as “NAT-yields” and which are anti-HBc negative. The outcome variable is whether or not blood donor has HBV infection. That is, a binomial variable. The predictor variables believed to be associated with HIV in blood donors will include greater number of recent sexual partners, recent scarification/tattoo/body markings, and history of personal contact with an HBV-infected

person. Other possible predictor variables, e.g., demographic variables, will be examined to understand their relationship to whether or not the blood donor has HBV infection. The association between the outcome variable and predictor variable will be examined using categorical data analysis techniques. Bivariate analysis will be conducted using Chi-square tests. Analyses that include more than one predictor variable will be conducted using multiple logistic regression, which may include interaction terms. In addition, nonparametric modeling will be used when there are multiple predictor variables.

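### Questionnaire item H5a asks about any non-injected drug without excluding dagga or whoonga, so among users of those drugs H5a to H5c and H6 are ambiguous

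*Protocol*

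**What the plan says.** Protocol, Appendix 7, Section H takes drugs in blocks. H3a asks "Have you ever used dagga, marijuana, or hashish", with first and last year in H3b and H3c. H4a asks "Have you ever used whoonga which is also known as nyaope", again with first and last year. H5a then asks "Have you ever used any non-injected drugs (drugs that are smoked, snorted or taken orally), examples include tik, mandrax", and goes on to glue, cocaine, methamphetamine, ecstasy and LSD. H5b and H5c ask for the first and last year of non-injected drug use. No item asks which drug was meant.

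Two skips matter. H1 (alcohol frequency) sends a respondent who never drinks to H4, so H3a to H3c are not asked. H5a = No goes to H7, which bypasses H6: "If you have smoked or snorted drugs, did you share pipes or straws with another person".

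Section 4.9 does not name drug use among the predictors for Objective 1a or 1b. For Objective 1a it falls under this provision: "Other possible predictor variables, e.g., behavioural variables, will be examined". Section 4.9 adds: "Analyses that include more than one predictor variable will be conducted using multiple logistic regression, which may include interaction terms".

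**The concern.** Smoked dagga and smoked whoonga meet H5a's definition of a non-injected drug. The named drugs are offered only as examples, and nothing tells the respondent to leave out what has already been reported. A dagga-only user who follows the definition answers Yes; one who follows the examples answers No. Both are fair readings.

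Elsewhere the questionnaire states its exclusions: C5 to C8a set aside HIV tests done at blood donation, D1 sets aside blood donation itself, and J20 sets aside cuts and scarification. H5a has no such phrase. The interview is in English only, in a country the Protocol describes as having eleven official languages (Section 4.4.1), and it is completed alone unless the respondent calls for help. Question order is therefore a weak guide to meaning.

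H5a is the only item on the donor's own non-injected use of the drugs it lists. Section 4.8.1 says the study wants to report across both common and less common behavioural exposures. If some Yes answers refer to dagga alone, the odds ratio for the other drugs may be diluted, and analysis cannot recover the split once interviews are done.

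**Working it through.** **1. What the answers establish.** The Protocol gives no prevalence, odds ratio or power for H5a, so there is no stated figure to reproduce. The items combine as follows.

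| H3a (dagga) | H4a (whoonga) | H5a | Can other-drug use be determined? |
|---|---|---|---|
| No | No | Yes | Yes, the answer is clear |
| Yes in at least one | | Yes | No: may be another drug, or the drug already reported |
| Not asked (never-drinker) | No | Yes | No: dagga alone is possible |

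In the last two rows the years in H5b and H5c may be those of dagga or whoonga. H6 is affected at its gate: two dagga-only smokers with identical histories are asked, or not asked, about sharing pipes according to how each read H5a.

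**2. Possible size (illustration).** From the Protocol: "300 incident HIV infected SANBS blood donors" and three controls per case (Section 4.1), giving 300 and 900; two-sided alpha 0.05 (Section 4.8.1). Assumed, because the Protocol gives none of them:
- share p of controls who used other drugs
- share d who used dagga only, with n = 1 − p − d
- odds ratios Ro (other drugs) and Rd (dagga only), both against neither
- fraction f of dagga-only users answering Yes, equal in cases and controls

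Observed H5a odds ratio = [(Ro·p + f·Rd·d) / (n + (1 − f)·Rd·d)] ÷ [(p + f·d) / (n + (1 − f)·d)].

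With Rd = 1 this reduces to (Ro·p + f·d) / (p + f·d).

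*Example A: p = 0.03, d = 0.15, Ro = 2.5, Rd = 1.*
- f = 0: 0.075 / 0.03 = 2.50
- f = 0.25: 0.1125 / 0.0675 = 1.67
- f = 0.5: 0.150 / 0.105 = 1.43
- f = 1: 0.225 / 0.18 = 1.25

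The share of Yes controls who used another drug, p / (p + f·d), is 44%, 29% and 17% at f = 0.25, 0.5 and 1.

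*Example A with Rd = 1.5.* At f = 0: (0.075 / 1.045) ÷ (0.03 / 0.97) = 2.32. At f = 0.25, 0.5 and 1 the result is 1.83, 1.71 and 1.67. The fall is much smaller.

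*Example B: p = 0.05, d = 0.10, Ro = 2.0; 300 cases, 900 controls, clinic clustering ignored.*

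| f | OR, Rd = 1 | Power | OR, Rd = 1.5 | Power |
|---|---|---|---|---|
| 0 | 2.00 | 0.77 | 1.90 | 0.71 |
| 0.25 | 1.67 | 0.64 | 1.76 | 0.73 |
| 0.5 | 1.50 | 0.53 | 1.70 | 0.77 |
| 1 | 1.33 | 0.39 | 1.67 | 0.85 |

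The rising power in the last column partly reflects dagga's own assumed effect; it is not better evidence on the other drugs.

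*Range over p = 3–10%, d = 5–20%, Ro = 2.0.*
- Rd = 1: 2.00 at f = 0; 1.38–1.89 at f = 0.25; 1.23–1.80 at f = 0.5; 1.13–1.67 at f = 1.
- Rd = 1.5: 1.80–1.95 at f = 0; 1.53–1.90 over f = 0.25 to 1.

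**The case against.** The best defence is that H5a is readable in context. Dagga and whoonga have their own blocks just before it, and neither is among its seven examples, so order and examples both point to other drugs. Nothing in the Protocol shows how many dagga-only users would answer Yes. The item supports no named hypothesis or power figure, and ACASI pilot testing is planned before enrolment (Section 4.11).

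Most of this stands. It makes mixing a possibility rather than an established fact, and it limits the weight of the point. It does not remove the literal definition, and the appeal to order fails for never-drinkers, who are not asked about dagga at all.

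A reader might go further and infer that the H5a odds ratio cannot be interpreted, or that H5a cannot be entered in a model with H3a. The Protocol does not support either. H5a is clear where H3a and H4a are both No; the three items are separate variables that the planned logistic regression can take together; and use of any non-injected drug can be built from all three. What is lost is the split among dagga and whoonga users, and among never-drinkers. Restricting to H3a = No and H4a = No gives a clean contrast, but drops everyone who used dagga or whoonga as well as another drug.

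**Conclusion.** The wording gap is real and limited. Dagga-only or whoonga-only users may answer H5a either way, no later item resolves it, and H5b, H5c and H6 inherit the ambiguity. The consequence is possible misclassification of an exploratory exposure.

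Any dilution runs from slight to heavy. It is heavy if dagga-only use is much commoner than other-drug use, carries little risk and is often reported under H5a; it is slight if dagga carries risk of its own or few dagga-only users answer Yes. These sizes rest entirely on assumed prevalences, an assumed dagga odds ratio and equal reading of the item by cases and controls. The documents support no single figure. The change is worth making because it is cheap and the lost information cannot be recovered after interview. The stated hypotheses and detectable odds ratios are not affected.

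**What to change.** Make four changes together, before the ACASI is piloted:

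1. Reword H5a, H5b and H5c to *any non-injected drugs other than dagga/marijuana/hashish or whoonga/nyaope*, keeping the examples.
2. Route H1 = Never to H3a. With the rewording alone, a never-drinker's dagga use would be recorded nowhere.
3. Ask H6 of anyone answering Yes to H3a, H4a or H5a. With the rewording alone, every dagga-only or whoonga-only smoker who answers No would be sent past the sharing item.
4. Analyse dagga, whoonga and other non-injected drugs as three separate exposures.

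Cost: a few words in three items, two changed skips, and a few extra questions for never-drinkers and for dagga or whoonga users.
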